### 3.3.3.6 Secondary Effectiveness Endpoints

- The rate of valve-related dysfunction, defined as moderate or severe prosthetic valve stenosis, or moderate or severe prosthetic regurgitation at one year (per VARC II)

The incidence estimate will be provided for the two treatment groups at the specified time point. The statistical method will be the Bayesian version of a comparison of proportions (with predictions). The incidence estimates will also be reported at the following time points: 30 days, 6 months, one year, 2 years, 3 years, 4 years, 5 years, 7 years and 10 years.

- Quality of Life as assessed by Kansas City Cardiomyopathy (KCCQ) change from baseline at 30 days and one year  
The endpoint will be evaluated using a Bayesian analog of a two-sample t-test or the non-parametric Wilcoxon rank-sum test. The descriptive statistics for KCCQ change from baseline will also be reported at 30 days, 6 months, one year, and annually thereafter through 5 years.
- The rate of repeat hospitalization for aortic valve disease at one year.

The incidence estimate will be provided for the two treatment groups at the specified time point. The statistical method will be the Bayesian version of a comparison of proportions (with predictions). In addition, the Kaplan-Meier estimates will be provided at the following time points: 30 days, 6 months, 12 months, and annually thereafter through 10 years.

- Device Success (VARC II), defined as
  - Absence of procedural mortality, AND
  - Correct positioning of a single prosthetic heart valve into the proper anatomical location, AND
  - Intended performance of the prosthetic heart valve, defined as the absence of patient-prosthesis-mismatch and mean aortic valve gradient less than 20 mmHg (or peak velocity <3 m/sec), AND absence of moderate or severe prosthetic valve regurgitation.

The incidence estimate will be provided for the TAVR group.

- Hemodynamic performance metrics by Doppler echocardiography
  - Mean aortic gradient at one year
  - Effective orifice area at one year
  - Degree of total, peri, and transvalvular prosthetic regurgitation at one year

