where  $\mu_{\text{TAVR}}$  and  $\mu_{\text{SAVR}}$  denote the mean changes in the KCCQ score from baseline to 1 year. For subjects with KCCQ score at both baseline and 1 year, the change in KCCQ will be calculated as  $\text{KCCQ}_{1\text{year}} - \text{KCCQ}_{\text{baseline}}$ . The objective will be evaluated using a Bayesian version of a two-sample t-test. The posterior probability  $P(H | \text{data})$  will be calculated and compared to a threshold of 0.95.

**Rationale for Delta:** A 5-point improvement or decrease in KCCQ is the minimum difference that is clinically relevant.

5. Transvalvular mean gradient at 1 year (superiority). The hypothesis of interest is

$$H: \mu_{\text{TAVR}} < \mu_{\text{SAVR}}$$

where  $\mu_{\text{TAVR}}$  and  $\mu_{\text{SAVR}}$  denote the average mean gradient at 1 year, measured in mmHg. This objective will be evaluated using a Bayesian version of a two-sample t-test. The posterior probability  $P(H | \text{data})$  will be calculated and compared to a threshold of 0.975.

6. Effective orifice area at 1 year (superiority). The hypothesis of interest is

$$H: \mu_{\text{TAVR}} > \mu_{\text{SAVR}}$$

where  $\mu_{\text{TAVR}}$  and  $\mu_{\text{SAVR}}$  denote the mean effective orifice area at 1 year, measured in  $\text{cm}^2$ . This objective will be evaluated using a Bayesian version of a two-sample t-test. The posterior probability  $P(H | \text{data})$  will be calculated and compared to a threshold of 0.975.

7. Change in Kansas City Cardiomyopathy Questionnaire (KCCQ) score from baseline to 30 days (superiority). The hypothesis of interest is

$$H: \mu_{\text{TAVR}} > \mu_{\text{SAVR}}$$

where  $\mu_{\text{TAVR}}$  and  $\mu_{\text{SAVR}}$  denote the mean changes in the KCCQ score from baseline to 30 days. For subjects with KCCQ score at both baseline and 30 days, the change in KCCQ will be calculated as  $\text{KCCQ}_{30\text{day}} - \text{KCCQ}_{\text{baseline}}$ . The objective will be evaluated using a Bayesian version of a two-sample t-test. The posterior probability  $P(H | \text{data})$  will be calculated and compared to a threshold of 0.975.

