### 3.3.4 Number of Subjects and Investigational Devices, Trial Duration

This trial will involve at least 1200 subjects in the AT population among all active sites. No site will implant more than 100 subjects without prior authorization from Medtronic. Subjects who exit from the trial after implantation will not be replaced.

Subjects will be consented for follow-up through 10 years. The enrollment period is estimated to be between 18 to 24 months; therefore the estimated total duration of the trial (first subject enrolled to last subject completing his/her last follow-up exam) is estimated to be 12 years. The number of investigational TAVR systems used in the trial is estimated to be between 600 and 700 (based on sample size and 1:1 randomization).

Randomization will continue until the required number of subjects in the LTI Sub-Study and the Japan addendum are met, up to 1540 randomized subjects.

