#### **Baseline/Pre-implant Required prior to Index Procedure**

- 12-lead ECG
- Complete blood count, creatinine,
- Modified Rankin Score
- Kansas City Cardiomyopathy Questionnaire (KCCQ)
- Euro-Qol (EQ-5D) Quality of Life survey
- Anti-thrombotic medications
- Adverse Events

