**30 days (between 30 to 45 days post implant)**

- Clinical assessment
- TTE
- 12 lead ECG
- Creatinine
- Modified Rankin Score
- KCCQ
- EQ-5D
- Anti-thrombotic medications
- I.N.R. (for subjects on VKA)
- Adverse Events

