## Notes:

1. DVI = Doppler Velocity Index (LVOT VTI/valve VTI)
  2. For subjects with BSA <1.6 m^2, the EOA criteria for significant (moderate or severe) stenosis is <0.6 cm^2
  3. For subjects with LVOT diameter >2.5 cm, the DVI criteria for significant (moderate or severe) stenosis is <0.2 cm^2
  4. Reporting of prosthetic valve dysfunction will be based on core lab results.
  5. Prosthetic valve dysfunction events are not reported as adverse events, unless the dysfunction is accompanied with clinical sequelae at the time of event detection, and the clinical sequelae are chronologically and physiologically associated with the dysfunction. However, prosthetic dysfunctions that are associated with adverse events, and that meet the definition of a serious adverse event, should be reported as such.
- Quality of Life as assessed by Kansas City Cardiomyopathy Questionnaire (KCCQ) at 30 days and one year  
The endpoint will be evaluated using a Bayesian analog of a two-sample t-test. Descriptive statistics for KCCQ change from baseline will also be reported at 30 days, 6 months, one year, and annually through 5 years.
  - The rate of repeat hospitalization for aortic valve disease at one year.  
The incidence estimate will be provided for the two treatment groups at the specified time point. The statistical method will be the Bayesian version of analysis for comparing proportions. In addition, the Kaplan-Meier estimates will be provided at the following time points: 30 days, 6 months, 12 months, 18 months, and annually thereafter through 10 years.
  - Device Success (VARC II), defined as
    - Absence of procedural mortality, AND
    - Correct positioning of a single prosthetic heart valve into the proper anatomical location, AND
    - Intended performance of the prosthetic heart valve, defined as the absence of patient-prosthesis-mismatch and mean aortic valve gradient less than 20 mmHg (or peak velocity < 3 m/sec), AND absence of moderate or severe prosthetic valve regurgitation.

The incidence estimate will be provided for the TAVR group.

The criteria for ECHO will be based on the ECHO Core Lab Data:

- Absence of patient-prosthesis-mismatch
  1. For subjects with BMI < 30 kg/m^2, index effective orifice area (EOAi) > 0.85 cm^2 /m^2
  2. For subjects with BMI ≥ 30 kg/m^2, index effective orifice area (EOAi) > 0.70 cm^2 /m^2

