where  $\mu_{TAVR}$  and  $\mu_{SAVR}$  denote the mean changes in the KCCQ score from baseline to 1 year. For subjects with KCCQ score at both baseline and 1 year, the change in KCCQ will be calculated as  $\text{KCCQ}_{1\text{year}} - \text{KCCQ}_{\text{baseline}}$ . The objective will be evaluated using a Bayesian version of a two-sample t-test. The posterior probability  $P(H | \text{data})$  will be calculated and compared to a threshold of 0.95.

This document is electronically controlled. Printed copies are considered uncontrolled.

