**Confidential**

**Rationale for Delta:** A 5-point improvement or decrease in KCCQ is the minimum difference that is clinically relevant.

5. Transvalvular mean gradient at 1 year (superiority). The hypothesis of interest is

$$H: \mu_{TAVR} < \mu_{SAVR}$$

where  $\mu_{TAVR}$  and  $\mu_{SAVR}$  denote the average mean gradient at 1 year, measured in mmHg. This objective will be evaluated using a Bayesian version of a two-sample t-test. The posterior probability  $P(H | \text{data})$  will be calculated and compared to a threshold of 0.975.

6. Effective orifice area at 1 year (superiority). The hypothesis of interest is

$$H: \mu_{TAVR} > \mu_{SAVR}$$

where  $\mu_{TAVR}$  and  $\mu_{SAVR}$  denote the mean effective orifice area at 1 year, measured in  $\text{cm}^2$ . This objective will be evaluated using a Bayesian version of a two-sample t-test. The posterior probability  $P(H | \text{data})$  will be calculated and compared to a threshold of 0.975.

7. Change in Kansas City Cardiomyopathy Questionnaire (KCCQ) score from baseline to 30 days (superiority). The hypothesis of interest is

$$H: \mu_{TAVR} > \mu_{SAVR}$$

where  $\mu_{TAVR}$  and  $\mu_{SAVR}$  denote the mean changes in the KCCQ score from baseline to 30 days. For subjects with KCCQ score at both baseline and 30 days, the change in KCCQ will be calculated as  $\text{KCCQ}_{30\text{day}} - \text{KCCQ}_{\text{baseline}}$ . The objective will be evaluated using a Bayesian version of a two-sample t-test. The posterior probability  $P(H | \text{data})$  will be calculated and compared to a threshold of 0.975.

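### The two KCCQ gates (change at 1 year and at 30 days) are tested without baseline KCCQ as a covariate, which gives up some precision ahead of the primary superiority claim

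*SAP*

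**What the plan says.** SAP 6.9.1 lists seven secondary objectives tested in a fixed order. Two of them concern KCCQ.

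- **Item 4** is non-inferiority at 1 year, with a margin of 5 points and a posterior threshold of 0.95. The outcome is a simple difference: "For subjects with KCCQ score at both baseline and 1 year, the change in KCCQ will be calculated as" the 1-year score minus the baseline score.
- **Item 7** is superiority at 30 days, with a threshold of 0.975. In Protocol 3.3.3.7.1 its parameters "denote the mean changes in the KCCQ score from baseline to 30 days".

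For both, the SAP says: "The objective will be evaluated using a Bayesian version of a two-sample t-test". SAP 6.8 gives the same method for the KCCQ endpoint: "The endpoint will be evaluated using a Bayesian analog of a two-sample t-test". Protocol 3.3.3.6 is slightly wider: "The endpoint will be evaluated using a Bayesian analog of a two-sample t-test or the non-parametric Wilcoxon rank-sum test". Neither document gives a covariate-adjusted KCCQ model. Covariate-adjusted models appear only in the poolability analyses of the primary endpoint (SAP 6.10).

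Protocol 3.3.9 lists the "Kansas City Cardiomyopathy Questionnaire (KCCQ)" among the assessments required before the index procedure.

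Under SAP 6.9, an objective is tested only if all earlier ones have passed. The seven objectives are evaluated once, when primary non-inferiority is established. Primary superiority comes after all seven and is the only test that may be decided later.

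**The concern.** A t-test on change scores is a baseline-adjusted comparison with the baseline slope fixed at 1. If the true slope is below 1, which is usual when a score is only moderately correlated with its own baseline, the fixed slope leaves baseline noise in the treatment difference that an estimated slope would remove.

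The position of the two tests gives this some weight. A miss on item 4 ends formal testing of items 5 to 7 and of primary superiority. A miss on item 7 ends formal testing of primary superiority. Neither can be repeated with more data. Item 4 is the more exposed, because at the first interim analysis only about 850 subjects can have 1-year scores (SAP 6.5.2). Primary non-inferiority is not affected.

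**Working it through.** **The plan's own figures.** The documents give no sample size, SD or power for either KCCQ test. The only sample size is for the primary endpoint, and it reproduces. Farrington–Manning at 15% per arm, margin 0.06, one-sided 0.05 and 85% power gives 515.2 per arm, so 516 per arm and 1032 in total. Then 1032/0.94 = 1098, consistent with the stated 1100, and the added 100 gives 1200. This supplies the sizes used below: 850/2 = 425 and 1200/2 = 600 per arm. With 6% missing these become about 400 and 564.

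**Variance.** Let s0 and s1 be the baseline and follow-up SDs and r their correlation. Per subject, in large samples:

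- change score: s0² + s1² − 2·r·s0·s1
- baseline-adjusted: s1²·(1 − r²)
- difference: (s0 − r·s1)², which is never negative

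With s0 = s1 the ratio of adjusted to change-score variance is (1 + r)/2. That is 0.65, 0.75 and 0.85 at r = 0.3, 0.5 and 0.7, or reductions of 35%, 25% and 15%.

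**Power.** Power = Φ(d/(SD·√(2/n)) − z), where n is per arm. With diffuse priors, thresholds of 0.95 and 0.975 correspond to z = 1.645 and 1.96. For the adjusted test, SD is multiplied by √((1 + r)/2). For item 4 with no true difference, d is the margin, 5. For item 7, d is the true difference. SD of change (20, 22, 24, 26, 28), r (0.3, 0.5, 0.7) and the true differences are assumptions.

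One cell in full, item 4 at SD 24, r = 0.5, n = 425:

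- Planned: SE = 24·√(2/425) = 1.646; 5/1.646 − 1.645 = 1.392; power 91.8%.
- Adjusted: SD = 24·√0.75 = 20.78; SE = 1.426; 5/1.426 − 1.645 = 1.862; power 96.9%.

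Smallest and largest gains over the grid:

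| Test | n per arm | True difference | Smallest gain (points) | Largest gain (points) |
|---|---|---|---|---|
| Item 4 | 425 | 0 | 1.2 (97.7% to 99.0%; SD 20, r 0.7) | 11.2 (83.1% to 94.3%; SD 28, r 0.3) |
| Item 4 | 400 | 0 | 1.5 | 12.1 |
| Item 7 | 600 | 3 | 6.3 | 18.5 |
| Item 7 | 600 | 5 | 0.6 (99.1% to 99.7%) | 9.8 (87.1% to 97.0%) |
| Item 7 | 600 | 8 | about 0 | 0.1 |
| Item 7 | 564 | 3 | 6.1 | 18.5 |
| Item 7 | 564 | 5 | 0.8 | 11.0 |
| Item 7 | 564 | 8 | about 0 | 0.2 |

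**Why item 7 uses about 600 per arm.** Protocol 3.3.4 says "The enrollment period is estimated to be between 18 to 24 months". For 1200 subjects at a uniform rate that is 67 to 50 per month. The 850th procedure falls at month 12.8 to 17.0, so the first look is at month 24.8 to 29.0. The 1200th procedure plus the 45-day end of the 30-day window falls at month 19.5 to 25.5. At either rate, all 1200 are past that window by the first look.

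**Type I error.** Simulation with 100,000 trials per cell, SD of change 24, r = 0.3/0.5/0.7:

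- Item 4, 425 per arm: adjusted 0.049/0.049/0.051; t-test 0.049/0.049/0.051.
- Item 7, 600 per arm: adjusted 0.025/0.026/0.025; t-test 0.025/0.025/0.025.

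Both are nominal within simulation error, so the thresholds can stay.

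**NYHA (item 3).** With margin 0.375 and 425 per arm, Φ(0.375/(SD·√(2/425)) − 1.645) is 99.99% at an assumed SD of 1.0 and 99.8% at 1.2. Adjustment has nothing to add there.

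**The case against.** The strongest reply is that this is a choice between two valid estimators. The change score already uses the baseline, no error rate is inflated, and the size of the gain rests on quantities the documents do not give. That is fair, and it is why the point is minor.

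**Unequal SDs.** The table assumes equal SDs. With k = s0/s1 the variance ratio is (1 − r²)/(1 + k² − 2·r·k). At k = 0.8 and r = 0.7 it is 0.98, and item 4 gains only 0.2 to 0.6 points. At k = r = 0.7 the gain is zero. At k = 1.25, r = 0.3 and SD 28 it is 14.8 points. The equal-SD figures are therefore one slice of a wider range. This stands, but no part of the range is a large-sample loss.

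**True effect in item 4.** If TAVR is 2 points better (r = 0.5), the gain is 0.03 to 1.8 points. If it is 1 point worse, still well inside the margin, power at SD 24 and r = 0.5 rises from 78.4% to 87.7%.

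**Sample sizes.** Subjects who die lack a follow-up score, and the 6% allowance does not cover them. SAP 6.5.2 does not say which subjects enter the secondary tests at the first look, so 600 per arm for item 7 is an inference. If item 7 used only 90% of the 850 (about 382 per arm), power at SD 20 and r = 0.5 would rise from 54.6% to 66.8% at a true difference of 3, and from 93.3% to 97.9% at 5.

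**Timing of baseline.** Baseline KCCQ is required before the procedure, not before randomization. Assignment is open, and the as-treated set groups subjects by first attempted procedure. The simulations took baseline as independent of arm, which the documents do not guarantee. That caveat stands, but it does not favour the planned test: the change score subtracts the same baseline with slope 1 and so carries any arm-related shift in baseline reporting in full.

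**Conclusion.** The point holds as a minor efficiency matter. The planned tests for items 4 and 7 are valid, but they discard information the trial collects from every analysed subject, at two gates that are evaluated once. The large-sample variance identity needs no assumed values. The power gains do: modest for item 4 at the first look, larger for item 7 if the 30-day difference is small, and essentially nil for item 7 if it is large. They also shrink towards zero as the true baseline slope approaches 1.

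**What to change.** Before the first interim analysis, change SAP 6.9.1 items 4 and 7 to a Bayesian normal linear model of KCCQ change on treatment and baseline KCCQ, with diffuse priors. Compare the posterior probability for the treatment coefficient with the existing criteria: greater than −5 at 0.95 for item 4, and greater than 0 at 0.975 for item 7. Keep the two-sample t-test as a supportive analysis. Make the matching edit for KCCQ in SAP 6.8 and in Protocol 3.3.3.6 and 3.3.3.7.1, which would also settle the Wilcoxon alternative that remains in Protocol 3.3.3.6. Leave NYHA as it is.

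The cost is wording in both documents and routine programming. Under Protocol 3.3.25, an amendment judged significant also goes to the regulators and the IRBs/ECs. No new data are needed, no subject is lost from the analysis, and the simulated thresholds for the primary endpoint do not change.

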## 6.10. Heterogeneity/Poolability

Incidence of the primary endpoint will be evaluated for poolability across key subgroups. In particular, the primary endpoint will be examined for differences in outcome between gender, and need for revascularization. Tests for these outcomes will be performed to evaluate potential interactions between treatment and gender, and between treatment and need for revascularization.

### 6.10.1. Geography Poolability Analysis

Poolability analyses may be conducted either with frequentist or Bayesian statistical methods. The analysis descriptions below are written with the language of frequentist methods. If Bayesian methods are used, analogous models will be employed, with non-informative prior distributions, and statements below such as “significant at the 0.15 level” can be understood to mean if the 85% equal-tailed Bayesian credible interval (BCI) for the parameter of interest excludes 0.

#### 6.10.1.1. Primary Endpoint by Geography

The interaction between geography (US vs. Other) and treatment on the probability of death or disabling stroke at 24 months will be compared using a Cox proportional hazard model. This analysis will be performed on the AT set. If the resulting test is significant at the 0.15 level, further exploratory analysis will attempt to identify covariates that may explain treatment effect differences between the regions. Otherwise, the data will be considered to be poolable across geographies.

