**Confidential**

sequential analysis plan using equal information increments and Pocock-type alpha spending, the sample size would have to be increased by about 15%, whereas an O'Brien-Fleming alpha spending approach would increase the total sample size by approximately 1%. The impact of the sampling plan used in this Bayesian design is likely to fall between these two approaches, so an additional 100 subjects (9%) will be accrued, bringing the total estimated sample size to 1200 as treated (AT) subjects, which should provide ample power for establishing non-inferiority in the primary hypothesis test.

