### **6.10.1.3. Multivariable Analysis**

Along with geography and treatment-by-geography interaction, any covariates with a 0.20 significance level from the Univariate Covariate Analysis will be included in a Cox proportional hazard model. If this multivariable regression does not result in a significant (level 0.15) geography by treatment interaction after adjustment for these baseline factors, then outcome results will again be considered poolable across geographies. If geography by treatment interaction is still significant (level 0.15) after adjustment for these factors, results will be presented by geography and the clinical significance of these differences will be assessed.

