#### **6.10.2.1. Pooling of Small Sites**

Sites should contribute to at least 5 treatment and at least 5 control subjects to the AT set. If this is not the case, the site is considered a “small site”; small sites will be ordered by the date of first procedure in the AT set. Starting with the first “small site”, a pseudo-site will be created by adding subjects from successive “small sites”. Once the number of subjects (treatment and control subject together) reaches or exceeds the size of the median enrollment (treatment and control subject together) of the “large sites”, then a second pseudo-site will be created, beginning with the next site not already included in the first pseudo-site. Additional pseudo-sites, if needed, would be created in the same manner.

If the geographic regions (US vs. Other) are considered to be poolable then the pseudo-sites can consist of small sites of both geographic regions. If however the regions are not considered to be poolable, then specific pseudo-sites for both regions need to be created. A separate site poolability analysis will be performed for both regions.

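### A non-significant geography-by-treatment test is read as poolability, although it would usually miss a non-US TAVR excess as large as the 6-point margin

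*SAP*

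**What the plan says.** SAP 6.10.1.1 examines "The interaction between geography (US vs. Other) and treatment on the probability of death or disabling stroke at 24 months" with a Cox model, and "This analysis will be performed on the AT set". There are two branches. "If the resulting test is significant at the 0.15 level, further exploratory analysis will attempt to identify covariates" is the first. The second is "Otherwise, the data will be considered to be poolable across geographies".

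If the first branch is taken, SAP 6.10.1.3 refits the model with selected baseline covariates. If the interaction is then no longer significant at 0.15, "then outcome results will again be considered poolable across geographies". Presentation by geography is promised only in the one remaining case, where the interaction is still significant after adjustment.

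SAP 6.10.1 gives the Bayesian equivalent of the 0.15 level as whether the "85% equal-tailed Bayesian credible interval (BCI) for the parameter of interest excludes 0", so the test is two-sided.

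The status carries forward. Under SAP 6.10.2, poolable regions mean that the site analysis disregards region. SAP 6.10.2.1 adds: "If the geographic regions (US vs. Other) are considered to be poolable then the pseudo-sites can consist of small sites of both geographic regions".

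Neither document gives a tolerable regional difference, a power for this test, or an expected US share.

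**The concern.** Calling two regions poolable is a conclusion of similarity. Failing to reject an interaction supports that only if the test had a good chance of finding a difference that matters, or if an interval excludes such a difference. The rule asks for neither.

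The obvious yardstick is the trial's own margin of 6 percentage points. If TAVR were worse than SAVR by that amount in one region and equal in the other, a reader would want to know. Under the rule, the likely result is a statement that the data are poolable, no commitment to show the regional estimates, and a site analysis that ignores region.

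There is also a mismatch of scale. The primary hypothesis (SAP 6.5.1) is an absolute difference; the poolability test is on a hazard ratio. Equal hazard ratios do not mean equal risk differences when control rates differ by region.

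**Working it through.** **Inputs from the documents.** SAP 5.2: "bringing the total estimated sample size to 1200 as treated (AT) subjects"; 15% incidence per arm; margin 0.06; 1:1 allocation. SAP 6.10.1: two-sided 0.15, critical z = 1.44. Protocol 3.3.4: up to 1540 randomized.

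**Assumed.** US share 50-80%; 15% vs 15% in the US; 21% TAVR vs 15% SAVR in Other; all subjects followed to 24 months.

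**The plan's own figure.** No power is stated for the interaction test. The nearest stated figure is the single-look sample size of 1032. The Farrington-Manning formula at 15% vs 15%, margin 0.06, 85% power and one-sided 0.05 gives 516 per arm, or 1032. The planning inputs therefore reproduce.

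**Effect to be detected.** On the hazard scale, the interaction is the log of the ratio of hazard ratios: ln[ln(1 - 0.21) / ln(1 - 0.15)] = ln(1.450) = 0.372.

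**Standard error.** The square root of the sum of 1/events over the four region-by-arm cells. At a 50% US share each cell has 300 subjects, so events are 63, 45, 45 and 45. The variance is 1/63 + 3/45 = 0.0825, SE = 0.287, and z = 0.372/0.287 = 1.29.

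**Probability of non-significance.** Phi(1.44 - 1.29) - Phi(-1.44 - 1.29) = 0.55 to 0.56.

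| US share | Events: Other TAVR, Other SAVR, US TAVR, US SAVR | SE | P(not significant) |
|---|---|---|---|
| 50% | 63, 45, 45, 45 | 0.287 | 0.555 |
| 60% | 50.4, 36, 54, 54 | 0.291 | 0.561 |
| 70% | 37.8, 27, 63, 63 | 0.309 | 0.589 |
| 80% | 25.2, 18, 72, 72 | 0.351 | 0.642 |

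Simulating the full Cox model gives 0.558 at an equal split and 0.619 with 75% of subjects in the US. With no interaction it rejects in 14.7% of runs, as it should at 0.15.

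**Sensitivity, US share 50-80%.**
- 6% fewer events through dropout: 0.57-0.65.
- 1540 subjects: 0.49-0.59.
- 10% base rate, 1200 subjects: 0.49-0.59. 5% base rate: 0.39-0.50.
- 850 subjects, all with 24 months: 0.63-0.70. At a real interim the event count depends on accrual, so this shows direction only: fewer events than at the final analysis means a higher miss rate.

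**Size needed.** An 80% chance of detection at an equal split would take about 3,730 subjects.

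**Scale.** Take a common hazard ratio of 1.4. At a 10% control rate, TAVR is 1 - 0.90^1.4 = 13.7%, an excess of 3.7 points. At 20% it is 1 - 0.80^1.4 = 26.8%, an excess of 6.8 points. One region is inside the margin and the other outside, with no hazard-ratio interaction to find at any sample size.

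**What regional estimates would show.** With 15% in both arms, the 95% half-width for the Other-region risk difference is 1.96 x sqrt(2 x 0.15 x 0.85 / n). For n = 300 per arm (50% US) this is 5.7 points; for n = 120 per arm (80% US) it is 9.0 points. The US half-widths are 5.7 and 4.5. For the between-region difference, sqrt(5.7^2 + 5.7^2) = 8.1 and sqrt(4.5^2 + 9.0^2) = 10.1 points.

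**The case against.** **The trial's decision does not depend on this rule.** This is correct and limits the point. Non-inferiority is declared from the posterior probability on all AT subjects (SAP 6.5.2), and neither that decision nor the hierarchy in SAP 6.9 refers to geography. Randomization is stratified by site, so arms are compared within region by design. A reader might infer that the rule lets the trial succeed wrongly, or might combine the chance of a pooled win with the chance of a poolable verdict. The documents do not support that use: the pooled win would occur whatever the interaction test showed, and the threshold Psi is not given in them.

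**The SAP does not claim proof.** It uses an operational phrase, and 0.15 is more lenient than 0.05, at which the same scenario would be missed in 75-81% of trials. The leniency deserves credit, but it is already in the figures above.

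**Regional results are not forbidden.** A reader might infer that a non-significant test removes them. SAP 6.10.1.3 only withholds the commitment. SAP section 7 separately promises a Japan report and a Japan vs non-Japan analysis once non-inferiority is shown. That covers about 50 AT subjects and does not answer the US vs Other question.

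**The miss rate is conditional.** It depends on an unstated split, the base rate and the sample size. This stands, and the ranges are part of the result.

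**Mixed pseudo-sites.** A reader might infer that they would hide a regional difference again. Only sites with fewer than 5 subjects in either arm are merged, and no calculation here shows such an effect.

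**Conclusion.** The concern holds as a matter of inference and reporting. The SAP turns a non-significant interaction into a positive statement of poolability, with no bound on the regional difference. The test behind it is non-significant in about 56-64% of trials when the non-US TAVR excess equals the whole margin. That range assumes 1200 AT subjects, a 15% base rate, no US excess and a US share of 50-80%. It falls to about 49-59% at 1540 subjects and 39-50% at a 5% base rate, and rises at an interim. The scale mismatch is a separate weakness. It does not drive these figures, because the SAVR rate was set equal in the two regions.

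What is affected is the poolability statement, the commitment to regional results, and whether the site analysis takes region into account. The primary conclusion is not affected. The change is worth making before the analysis, but it is not a condition for the validity of the primary test.

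**What to change.** - In SAP 6.10.1.1 and 6.10.1.3, replace the poolability conclusion with wording that no heterogeneity was detected and that pooling is pre-specified by design.
- Whatever the test shows, report the 24-month TAVR minus SAVR risk difference with a 95% Bayesian credible interval in the US and in Other, and the between-region difference in risk differences with its interval. This puts the regional evidence on the scale of the 0.06 margin.
- Keep the 0.15 test only as the trigger for covariate exploration.

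The cost is a wording change and one table. Hypothesis, sample size and conduct are untouched. The downside is that imprecise regional estimates appear even when no interaction is detected. With half-widths of about 5.7-9.0 points in the Other region, they should be labelled as descriptive and not read as regional non-inferiority tests.
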